5.2 SAFETY ANALYSIS SET

N/A

5.3 OTHER ANALYSIS SET

N/A

5.4 SUBGROUPS

Subgroup analyses will be conducted on the whole dataset according to the treatment lines groups defined below:

- First Line (palbociclib prescribed as the first line treatment for metastatic breast cancer)
- First line palbociclib added to letrozole (palbociclib prescribed as the first line treatment and added to letrozole which is ongoing at index and prescribed more than 3 months prior to initiation on palbociclib)
- Second line (palbociclib prescribed as the second or later treatment line (in the clinician's/Pfizer's opinion) for metastatic breast cancer)

[figure not shown]
6 ENDPOINTS AND COVARIATES

The following endpoints will be estimated for the final report. Additional endpoints evaluated as a result of decisions made by the CI and Pfizer have been italicized. This list is designed to reflect the analyses conducted.

Primary Objective: To describe patient demographic and clinical characteristics at initiation of palbociclib.

- Age at initiation of palbociclib.
- Distribution of treatment lines
- Time to letrozole – 1st line palbociclib group
- Sex (male/female)
- Ethnicity of patients initiated on palbociclib.
- Menopausal status at initiation of disease
- Menopausal status at recurrence of disease
- Menopausal status at diagnosis of metastatic disease
- Disease free interval
- Summary measures of MBC history, including:
 - Whether cancer is primary or recurrent diagnosis.
 - Site and grade of disease.
 - Lymph node involvement (including number of lymph nodes) at initial BC diagnosis and by de novo status
 - Oestrogen-receptor, progesterone-receptor and HER2 status at initiation of disease

PFIZER CONFIDENTIAL

- Oestrogen-receptor, progesterone-receptor and HER2 status in the metastatic setting
- Proportion of patients (non de-novo metastatic only) who had a rebiopsy
- Oestrogen-receptor, progesterone-receptor and HER2 status at recurrence of disease out of those patients who were rebiopsied.
- Tumour stage at initial disease diagnosis and by de novo status
- Nodal status at initial disease diagnosis and by de novo status
- Metastatic at initial disease diagnosis and by de novo status
- Tumour size at initiation of disease and by de novo status
- Tumour grade at initiation of disease and by de novo status
- Proportion of patients who had Ki67 measured
- Summary of Ki67 values out of those patients with Ki67 measured.
- ECOG performance score at initial disease diagnosis
- ECOG performance score at recurrent disease diagnosis
- ECOG score at metastatic diagnosis
- Type of recurrence
- Number of metastatic sites.
- Location of metastases
 - Non-visceral location of metastases
 - Metastatic sites with locoregional recurrence
- Duration of BC disease at initiation of palbociclib.
 - Defined as date of diagnosis to date of initiation of palbociclib.
- Treatment history of MBC
 - Proportion of patients treated with chemotherapy in the neoadjuvant or adjuvant setting
 - Chemotherapy name
 - Proportion of patients treated with chemotherapy in the advanced/disease modification/metastatic setting
 - Chemotherapy name
 - Number of lines of prior chemotherapy for metastatic disease
 - Proportion of patients for whom an LHRH was used
 - Proportion of patients treated with endocrine therapy in the neoadjuvant or adjuvant setting
 - Endocrine therapy name
 - Proportion of patients treated with endocrine therapy in the advanced/disease modifying/metastatic setting
 - Endocrine therapy name
 - Number of lines of prior endocrine therapy for metastatic disease
- Proportion of patients treated with radiotherapy in the advanced/disease modifying/metastatic setting
- Concomitant medications (defined as medications prescribed whilst on palbociclib)
- Concomitant medications prescribed alongside goserelin

PFIZER CONFIDENTIAL

- Number of prior treatments in the metastatic setting, all prior therapies as well as chemotherapy/endocrine therapy combined and separately

[figure not shown]
Secondary Objective 1: To describe treatment pattern (as per licence/IPP requirement); including the proportion of patients with dose modification and who switch treatment 1, 2 and 3 years after palbociclib initiation, and median time to dose modification and treatment discontinuation ('drug survival'). For patients who progress, to describe the 1st /2nd /3rd line of treatment after progression.

- Summary measures of palbociclib treatment patterns including:
 - Starting Dose.
 - Endocrine partner prescribed alongside palbociclib
 - Proportion of patients with dose reductions at 1, 2 and 3 years after initiation.
 - Proportion of patients with palbociclib treatment discontinuation at 1, 2 and 3 years after initiation.
 - Reasons for discontinuation of palbociclib
 - Proportion of patients with temporary discontinuations
 - Time to dose reduction in number of days (from start of treatment) – 1st line treatment group only
 - Time to palbociclib discontinuation ('drug survival') in number of days (from start of treatment) in those patients permanently discontinuing palbociclib
 - Reasons for discontinuation.
 - 1st, 2nd, and 3rd line of treatment after progression: number of patients prescribed each medication, dose, and length of treatment.
- Description of the number of patients which are being prescribed as per posology of treatment.
 - Number of completed 28-day cycles per patient.
 - Proportion of patients co-administered letrozole at palbociclib initiation.
 - Proportion of patients co-administered fulvestrant at palbociclib initiation.

Secondary Objective 2: To describe overall survival and progression-free survival, response (CR, PR), stable disease. This includes estimating the proportion of patients achieving those endpoints at 1, 2 and 3 years following palbociclib initiation; median survival, time to response and duration of response. In patients who respond to treatment, to describe PR and CR using "swimmer plots".

- Proportion of patients at 2-years following initiation of palbociclib who:
 - Are free from disease progression.
 - Are alive
 - Achieved PR
 - Achieved CR
 - Had stable disease
- Median (95% confidence interval [CI]):
 - PFS

PFIZER CONFIDENTIAL

- OS
 - Time to achieving best overall response
- Length of follow-up
- Best response to palbociclib, overall and by de novo and relapse status
- Time to best response – by de novo and relapse status
- Time to first response – overall and by de novo and relapse status

Secondary Objective 3: To describe the occurrence of neutropenia during the first-year post-initiation observation period.

- In the 6 months post-palbociclib initiation, proportion of patients who experience,
 - Neutropenia (overall and by grade, recorded and inferred from ANC measurements).
 - Worst neutropenia experienced within 3 months of palbo initiation
 - Febrile Neutropenia.

[figure not shown]
Secondary Objective 4: To describe the occurrence of gastro-intestinal toxicity, including diarrhoea, nausea and vomiting during the first-year post-initiation observation period.

- For each cycle, proportion of patients who experience Gastro-intestinal toxicity, including:
 - Diarrhoea.
 - Severity
 - Nausea.
 - Severity
 - Vomiting.
 - Severity
- Proportion of patients experiencing an AE during follow-up

Secondary Objective 5: To describe progression of clinical indicators, including biochemical and radiological indicators at each time-point available during the first year following palbociclib treatment initiation.

- Summary measures of full blood counts in the first 6 months following initiation:
 - Haemoglobin.
 - White cell counts.
 - Absolute neutrophil counts.
 - Platelet counts.
- Summary measures of liver function tests in the first 6 months following initiation:
 - aspartate transaminase (also called aspartate aminotransferase).
 - alanine transaminase (also called alanine aminotransferase).
 - alkaline phosphatase.
 - Albumin
 - Bilirubin

PFIZER CONFIDENTIAL

[figure not shown]
- Summary measures of bone profile in the first 6 months following initiation:
 - Calcium.
 - Phosphate.
- Summary measures of urea and electrolytes in the first 6 months following initiation:
 - Creatinine
 - Potassium
 - Sodium
 - Urea
- Summary measures of radiological indicators in the first 6 months following initiation including the proportion of patients with:
 - Stable disease.
 - Progressive disease.
 - CR or PR.

Secondary Objective 6: To describe BC-related healthcare resource utilisation during the first year following palbociclib initiation.

- Summary measures of hospital admissions for each line of therapy, including:
 - Proportion of patients with at least one inpatient admission recorded
 - Inpatient admissions per patient.
 - Elective or non-elective.
 - Reasons for admission (including day cases).
 - Length of stay per inpatient admission.
 - Proportion of patients with at least one outpatient visit recorded
 - Outpatient visits per patient.
 - Reason for outpatient visit
 - Type of HCP seen during outpatient visits
- Proportion of patients with at least one interaction with CNS
- Number of CNS interactions per patient
- Type of CNS interaction
- Reason for CNS interaction
- Proportion of patients with at least one interaction with AOS
- Number of AOS interactions per patient
- Type of AOS interaction
- Reason for AOS interaction

For the estimation of endpoints, *the following definitions will be implemented. PFS will be defined as the time from the date of palbociclib initiation to the date of first documented disease progression (as documented in the radiological assessment section of the eCRF) or death. OS will be defined as the time from the date of palbociclib initiation until death from any cause. Time to achieving best overall response will be defined in patients who respond to treatment as the time from the date of palbociclib initiation until*

PFIZER CONFIDENTIAL

achievement of the best overall response: CR, or PR if CR is not achieved during follow-up. Duration of response will be defined as the time from the date CR or PR was first documented (whichever is recorded first) to the date of first documented disease progression or death from any cause (whichever occurs first).

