The analysis will be descriptive. Demographic characteristics and medical history will be described at the time of palbociclib initiation (baseline). Qualitative variables will be described by the absolute and relative (%) frequency of each class. Missing data will not be taken into account in the calculation of percentages (counts of missing observations will be included in a separate category). Quantitative variables will be described by their mean, standard deviation, median, 1st and 3rd quartiles, and extreme values (minimum and maximum), where applicable and the number of missing and non-missing values. The Kaplan-Meier method will be used to obtain estimates of median PFS, OS, CR, PR and time to discontinuation of palbociclib, with corresponding two-sided 95% confidence intervals.

Completion of retrospective data collection is planned for the 1st of February 2019. Completion of the prospective data collection is planned for the 1st of February 2021. An interim report on descriptive characteristics of patients already enrolled into the study (primary objective) will be produced in January 2019. Delivery of a 1-year report on the analysis of patients with 1-year follow-up post-initiation period (primary and secondary objectives) is planned for the 1st of July 2019. An additional 3-year report on the analysis of patients with up to 3-year follow-up post-initiation period (primary and secondary objectives) may be provided in July 2021.

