Definitions will be implemented as described in section 9.3 Variables. Patients who are known to be alive at the date of data collection (1-year for interim report and 3-year for full study report) will be censored at the date of data collection, and patients who are lost to follow-up will be censored on the date they were last known to be alive (e.g. date of last recorded hospital visit). Patients who are alive and free from disease progression at the date of data collection and those lost to follow-up will be censored on the date they were last known not to have disease progression (i.e. the date of last documented response assessment). Patients remaining in CR or PR at the end of the post-initiation observation period or lost to follow-up will be censored on the date CR or PR was last documented.

For the estimation of the proportion of patients alive, and free from disease progression, the denominator will be all patients known to be alive at the selected time-points (1 years, 2 years and 3 years). For the estimation of the proportion of patients achieving PR, CR and with stable disease at the selected time-points (1 years, 2 years and 3 years), the denominator will be all patients with at least one assessment of response (CR / PR / no response or stable disease / progressive disease) in the past year. Estimation of time to achieving best overall response and duration of response; and representation using swimmer plots will be performed in patients who respond (achieve CR or PR during follow-up) only.

Median PFS, OS, time to achieving best overall response, time to palbociclib dose modification and time to palbociclib discontinuation, and corresponding 95% CIs, will be estimated using Kaplan-Meier curves. Assessments of response (CR / PR / no response or stable disease / progressive disease) in patients responding to treatment (achieving CR or PR following initiation of palbociclib) will be represented using “swimmer plots”.

All percentages will be reported to the nearest whole number; therefore, in reporting study results in tables, figures and associated text, percentages may not add up to 100% due to rounding.

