8.1.3 Analysis for binary endpoints

Most binary endpoints will be summarised using frequency tables with percentages. For survival-related endpoints, Kaplan-Meier analysis may be used with proportions of patients reaching an event after different time periods and median survival (the time at which 50% of patients have reached a given endpoint out of all patients that are still being followed-up at that point or have reached that given end point) with 95% confidence intervals estimated using the method of Brookmeyer and Crowley⁶ or another appropriate method⁷. Swimmer plots will be used to show individual patient response to treatment over time (CR, PR, stable disease, progressive disease); these are plots that display a range of information with bars indicating the length of follow-up for each individual patient and symbols on the bars showing where CR and PR are reached and end.

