Proposed: Starting and mean dose of palbociclib and subsequent treatments after progression, length of treatments and time to dose reduction and discontinuation of palbociclib in days will be summarised as quantitative variables (see section 8.1.1). Times will be calculated in days through subtracting the time of first dose reduction/discontinuation from the date of palbociclib initiation. Treatment after progression and reasons for discontinuation, the proportion of patients completing a daily cycle, having dose reductions, treatment discontinuation and being co-administered letrozole and fulvestrant at palbociclib initiation will be summarised as categorical variables using frequencies and percentages (see section 8.1.2). Reasons for discontinuation of palbociclib will be presented as categorical data (see section 8.1.2) The proportions of patients with dose reductions and discontinuation will be calculated separately at 1 and 2 years after palbociclib initiation. Quantitative discrete variables (such as the number of completed cycles per patient) will be summarised using a combination of the approaches described in sections 8.1.1 and 8.1.2, if appropriate.

Actual: Starting dose of palbociclib was presented as a categoric variable as per section 8.1.2. Endocrine partner prescribed alongside palbociclib, proportion of patients with recorded dose reductions, proportion of patients who discontinued palbociclib and the associate reasons, proportion of patients with temporary interruptions to palbociclib treatment were presented as categoric variables as per section 8.1.2. Time to dose reduction was presented as a categoric variable as per section 8.1.2 (Categories: Patient did not have a dose reduction, dose reduction occurred within 3 months of palbociclib initiation, dose reduction occurred between 3 and 6 months after palbociclib initiation and dose reduction occurred over 6 months after palbociclib initiation). Number of patients

PFIZER CONFIDENTIAL

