prescribed treatment in the 1st, 2nd, and 3rd line after palbociclib discontinuation was presented as a categoric variable as per section 8.1.2. Dose, duration of subsequent treatments and number of completed 28-day cycles per patient were presented as quantitative variables as per section 8.1.1. Number of completed 28-day cycles (categories: 1-6 cycles, 7-12 cycles, 13-18 cycles, 19-24 cycles, 25-27 cycles and No completed cycles) and the proportion of patients co-administered letrozole or fulvestrant were presented as categoric variables as per section 8.1.2. All other endpoints were evaluated as proposed.

8.2.3 Secondary Objective 2: To describe overall survival and progression-free survival, response (CR, PR), stable disease. This includes estimating the proportion of patients achieving those endpoints at 1 and 2 following palbociclib initiation: median survival, time to response and duration of response. In patients who respond to treatment, to describe PR and CR using “swimmer plots”.

Proposed: For the estimation of the proportion of patients alive, and free from disease progression, the denominator will be all patients known to be alive at the selected time-points (e.g., 1 years, 2 years, and 3 years). For the estimation of the proportion of patients achieving PR, CR and with stable disease at the selected time-points (1 years and 2 years), the denominator will be all patients with at least one assessment of response (CR / PR / no response or stable disease / progressive disease) in the past year.

[figure not shown]
Actual: Proportion of patients free from disease progression, are alive, achieved PR, CR or stable disease were analysed separately at the 2-year timepoint only. Length of follow-up, and time to best response and first response were presented as quantitative variables as per section 8.1.1. Best response to palbociclib, overall and by de novo and relapse status was treated as a categoric variable and analysed according to section 8.1.2.

8.2.4 Secondary Objective 3: To describe the occurrence of neutropenia during the first-year post-initiation observation period.

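### The SAP reports drug survival only among patients who stopped palbociclib, with no censoring, so the median is biased downward; the protocol planned a Kaplan-Meier median

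*SAP*

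**What the plan says.** Protocol section 4 states: "The Kaplan-Meier method will be used to obtain estimates of median PFS, OS, CR, PR and time to discontinuation of palbociclib". Protocol section 9.7 repeats this: "time to palbociclib dose modification and time to palbociclib discontinuation, and corresponding 95% CIs, will be estimated using Kaplan-Meier curves". Secondary objective 1 asks for the median of both times and calls time to discontinuation drug survival.

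SAP section 6 lists the endpoint as "Time to palbociclib discontinuation ('drug survival') in number of days (from start of treatment) in those patients permanently discontinuing palbociclib". In SAP section 8.2.2 the proposed method is plain: "length of treatments and time to dose reduction and discontinuation of palbociclib in days will be summarised as quantitative variables". The account there of what was actually done does not mention time to discontinuation and closes with "All other endpoints were evaluated as proposed". The table in SAP section 8.2.9 gives it mean, median, SD, IQR and range. The same table names Kaplan-Meier for progression-free survival (PFS), overall survival, time to best response and duration of response.

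The censoring rules in SAP section 8.2 cover survival, progression and response. None covers a patient still taking palbociclib. SAP section 8.1.3 is only permissive ("For survival-related endpoints, Kaplan-Meier analysis may be used") and does not name discontinuation. SAP sections 5.1 and 8.1 set the analysis on 2-year data.

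The SAP keeps two other persistence outputs: "Proportion of patients with palbociclib treatment discontinuation at 1, 2 and 3 years after initiation" (section 8.2.2 proposes years 1 and 2 only) and completed 28-day cycles per patient.

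**The concern.** A median taken only among patients who stopped inside the window describes early stoppers. It does not describe how long the cohort stayed on treatment. Every patient still on drug at the cut has a longer time than is recorded, and exactly those patients are removed. The SAP still states the objective as median drug survival, so a reader will take the figure as that.

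Treatment persistence is a named focus of the study (Protocol section 7, SAP section 2), and results are split by treatment line (SAP sections 5.4 and 8.2.9). Because the bias grows with persistence, it also compresses differences between those groups. The report could show about half the cohort still on treatment at 2 years beside a drug-survival median of about 10 months.

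**Working it through.** **Direction.** Let F be the distribution of time to permanent discontinuation and 24 months the follow-up. The discontinuers-only median is the time t with F(t) = F(24)/2. If anyone is still on treatment at 24 months, F(24) is below 1, so F(t) is below 0.5 and t lies below the true median. This needs no distributional assumption.

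**Inputs.**
- Follow-up of 24 months: SAP sections 5.1 and 8.1.
- N of about 200: SAP section 2.1 (SAP section 5 says about 250).
- True median m: not given anywhere. As assumed stand-ins I use the palbociclib-arm PFS medians in Protocol section 7: 20.2 and 24.8 months (with letrozole) and 9.5 months (with fulvestrant).
- Shape: exponential, with Weibull shapes 0.8 and 1.3 as sensitivity. Follow-up is taken as complete.

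**Formulas (exponential).** F(24) = 1 − 2^(−24/m), and t = −m × log2(1 − F(24)/2).

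- m = 9.5: F(24) = 0.826; t = −9.5 × log2(0.587) = 7.31.
- m = 20.2: F(24) = 0.561; t = −20.2 × log2(0.719) = 9.60.
- m = 24.8: F(24) = 0.489; t = −24.8 × log2(0.756) = 10.02.

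| True median (months) | Dropped of 200 | Reported, exponential | Too low by | Reported, Weibull 0.8 to 1.3 |
|---|---|---|---|---|
| 6 | 12–13 | 5.5 | 9% | 4.8 to 5.9 |
| 9.5 | 35 | 7.3 | 23% | 6.1 to 8.5 |
| 12 | 50 | 8.1 | 32% | 6.6 to 9.7 |
| 15 | 66 | 8.8 | 41% | 7.1 to 10.7 |
| 20.2 | 88 | 9.6 | 52% | 7.7 to 11.7 |
| 24.8 | 102 | 10.0 | 60% | 8.1 to 12.3 |

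For true medians of 9.5 to 24.8 months, the shortfall over the Weibull shapes runs from 11% to 68%. Under the exponential the reported figure can never exceed 12 months, because the times of those who stop become uniform over 0 to 24 months as m grows.

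**Contrast between groups.** True medians of 24.8 and 9.5 months have a ratio of 24.8/9.5 = 2.6. The reported medians would have a ratio of 10.02/7.31 = 1.4.

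**Is the window binding?** The top cycle band in SAP section 8.2.2 is 25 to 27 completed cycles. That is 25 × 28 = 700 to 27 × 28 = 756 days, or 23.0 to 24.8 months, so some patients appear to have been treated to about the end of the window. Extending follow-up to 24.8 months changes little: the exponential results become 7.4, 9.8 and 10.3 months for true medians of 9.5, 20.2 and 24.8.

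**Does the protocol's estimator repair it?** In simulations with n = 200, 24 months and an assumed 10% per year loss to follow-up, Kaplan-Meier gave 5.97, 11.99 and 20.05 months for true medians of 6, 12 and 20. The discontinuers-only median in the same data was 5.2, 7.7 and 9.1.

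**Will the Kaplan-Meier median be reached?** With complete follow-up it is not reached if fewer than 100 of 200 stop by 24 months. P(Bin(200, F(24)) ≤ 99) is 0.60 for m = 24.8, 0.035 for 20.2 and below 0.001 for 9.5. Over the Weibull shapes it is 0.57 to 0.63 for 24.8 and 0.01 to 0.07 for 20.2. With 24.8 months of follow-up the first figure falls to 0.47.

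**The case against.** The strongest reply is that the report still conveys persistence. Completed cycles per patient are summarised for all patients, not just those who stopped. With complete follow-up and a true median below 24 months, the median of those cycles is not distorted by the cut: ignoring interruptions, 9.5 months is about 10 completed cycles and 20.2 months about 21. The 2-year proportion discontinued would then equal one minus Kaplan-Meier persistence at 24 months. This stands as mitigation. It weakens with interruptions, missing cycle dates and loss to follow-up, gives no confidence interval, and leaves a figure labelled drug survival that can contradict it.

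Second, Protocol section 9.7 lets the SAP modify the plan and ties amendments to primary endpoints, and SAP section 6 states the restriction openly. That is true, and nothing is concealed. But the SAP kept the objective of a median time to discontinuation, and this summary does not estimate it.

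Third, the sizes rest on PFS medians used as proxies, and the 9.5-month one comes from a fulvestrant trial, whereas the access programme was for use with an aromatase inhibitor. That is fair: the sizes and the 2.6 versus 1.4 contrast are illustrations, and no between-line test is planned. The direction does not depend on them.

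**Conclusion.** The concern holds. The SAP replaces a censored median with an uncensored summary in permanent discontinuers, and the result is biased downward whenever anyone is still on palbociclib at the cut. Under the assumptions above the shortfall is about 9% at a true median of 6 months, about a third at 12, and 52% to 60% at 20.2 to 24.8. Actual persistence is not in the documents, so the true position in that range is unknown. This should be fixed, but it concerns one secondary endpoint of a descriptive study.

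Time to dose reduction is a separate and milder matter. The categories actually reported keep patients without a reduction ("Patient did not have a dose reduction, dose reduction occurred within 3 months of palbociclib initiation"), so that output does not have this flaw. However, section 6 limits it to the first-line group, while section 8.2.9 lists plain summary statistics overall and by line, and the Kaplan-Meier median planned in the protocol is not given.

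**What to change.** Amend SAP sections 6, 8.2.2 and 8.2.9. Because the SAP describes analyses already done, also add a supplementary run to the report:

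- Estimate time to permanent discontinuation by Kaplan-Meier in the full analysis set and by treatment line. Censor patients still on palbociclib at the last date they are known to be on treatment.
- State that death on treatment counts as an event; the protocol is silent on this.
- Report the median with 95% CI or as not reached, plus Kaplan-Meier persistence with 95% CI at 12 and 24 months. The persistence estimates matter because the median may not be reached.
- The discontinuers-only summary may stay as a secondary description, but not under the name drug survival.
- For dose reduction, keep the categories, reconcile the population between sections 6 and 8.2.9, and add the planned Kaplan-Meier median or state that it was not reached. If patients are censored at permanent discontinuation, say that this treats a competing event as independent censoring.

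The cost is SAP wording, one Kaplan-Meier run on start, stop and last-visit dates that the protocol already collects, and one relabelled table row. No new data are needed.

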
• Summary measures of palbociclib treatment patterns, including:
○ Starting dose.○ Proportion of patients with dose reductions at 1, 2 and 3 years after initiation.○ Proportion of patients with palbociclib treatment discontinuation at 1, 2 and 3 years after initiation.○ Mean (Standard Deviation [SD]) dose intensity over the course of treatment in patients who complete treatment of palbociclib○ Median time to dose reduction in number of days (from start of treatment) and in terms of number of cycles (completed or interrupted).○ Median time to dose increase in number of days (from start of treatment) and in terms of number of cycles (completed or interrupted); only in patients with previously reduced dose○ Median time to palbociclib discontinuation ('drug survival') in number of days (from start of treatment) and in terms of number cycles (completed or interrupted).○ Reasons for discontinuation.○ 1st, 2nd and 3rd line of treatment after progression: number of patients prescribed each medication, dose, and length of treatment.• Description of the number of patients which are being prescribed as per posology of treatment (19):
○ Proportion of patients who complete a 28-day cycle (21 days daily dose followed by 7 days off treatment).○ Mean (SD) of completed 28 day cycles.○ Proportion of patients co-administered letrozole at palbociclib initiation.○ Proportion of patients co-administered fulvestrant at palbociclib initiation.	
• Palbociclib: date on initiation, initial dose, date of dose reduction, subsequent dose, dates of cycle initiation and completion, date of discontinuation (indicate whether last cycle is interrupted or completed), reasons for palbociclib dose reduction / increase / discontinuation.• Date of start and end of concomitant medication treatment: letrozole, fulvestrant, osteo-strengthening drugs (denosumab, zometa), other drugs.• First 3 lines of medication after palbociclib discontinuation: name, dose and length of treatment.

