8 STATISTICAL METHODOLOGY AND STATISTICAL ANALYSES

8.1 STATISTICAL METHODS

[figure not shown]
The following statistical methods will be used:

Full analysis will be conducted on 2-year follow up data not 3-year follow up data.

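### The SAP describes conformity with the 28-day schedule by a count of completed cycles that has no denominator, so conformity is mixed with time on treatment and follow-up.

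*SAP*

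**What the plan says.** - SAP section 6, Secondary Objective 1, has the item "Description of the number of patients which are being prescribed as per posology of treatment". Three measures stand under it: "Number of completed 28-day cycles per patient", and co-administration of letrozole and of fulvestrant. The last two concern the partner drug, so only the first bears on the cycle schedule. Section 6 says of its endpoint list: "This list is designed to reflect the analyses conducted".
- SAP 8.2.2 (Actual) reports the count as a quantitative variable and in bands: "Number of completed 28-day cycles (categories: 1-6 cycles, 7-12 cycles, 13-18 cycles, 19-24 cycles, 25-27 cycles and No completed cycles".
- Protocol 9.3 has two cycle measures under the same item: "Proportion of patients who complete a 28-day cycle (21 days daily dose followed by 7 days off treatment" and "Mean (SD) of completed 28 day cycles". SAP section 6 keeps a form of the second and leaves out the first.
- The first is still present elsewhere. SAP 8.2.2 (Proposed) includes it, worded as a daily cycle, and the 8.2.9 table lists it for a 28-day cycle. 8.2.2 (Actual) closes by saying that endpoints it does not name were handled as proposed.
- Protocol 9.3 collects the cycle-level data: "dates of cycle initiation and completion, date of discontinuation (indicate whether last cycle is interrupted or completed".
- SAP 8.1 fixes the window: "Full analysis will be conducted on 2-year follow up data not 3-year follow up data".

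**The concern.** The item asks how many patients were treated to the posology. A raw count of completed cycles answers a different question unless it is set against the number of cycles started or due. It grows with time on drug and is capped by the data window, and neither has to do with whether cycles ran as described. No rule says when a delayed or interrupted cycle counts as completed.

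The risk is that the count is published as evidence of schedule conformity. SAP 8.2.9 tabulates it overall and by treatment line. Protocol section 7 cites median PFS of 24.8 months for first-line use with letrozole and 9.5 months for second- or later-line use with fulvestrant. PFS is not time on treatment, but a lower cycle count in the later-line group would be expected even if both groups kept to the schedule equally well.

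**Working it through.** The documents give no figure to reproduce here, and the study size is pragmatic. The check is arithmetic on the count, followed by a simulation with assumed inputs.

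**1. Ceiling set by the window.** Maximum completed cycles = floor(days / 28). One year: 365.25/28 = 13.04, so 13. Two years: 730.5/28 = 26.09, so 26. The top band of 25-27 cycles spans 25 × 28 = 700 to 27 × 28 = 756 days, so on 2-year data it is in effect the band for patients treated throughout.

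**2. Count by time on treatment and conformity.** Cycles that fit = floor(months × 30.4375 / 28). Completed = floor(cycles that fit × share completed as described).

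| Months on drug | Cycles that fit | 100% | 90% | 75% | 50% |
|---|---|---|---|---|---|
| 6 | 6 | 6 | 5 | 4 | 3 |
| 12 | 13 | 13 | 11 | 9 | 6 |
| 18 | 19 | 19 | 17 | 14 | 9 |
| 24 | 26 | 26 | 23 | 19 | 13 |

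Down the 100% column conformity is constant, yet the count runs from 6 to 26 and the band from 1-6 to 25-27. The value 13 appears twice: 12 months at full conformity and 24 months at half. A patient who stops at 6 months with 6 of 6 completed (100%) is in band 1-6; one with 13 of 26 completed (50%) is in band 13-18.

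**3. Delays.** If every cycle starts 7 days late (35-day intervals), floor(730/35) = 20 cycles are completed in two years. A patient exactly on schedule who stops at day 20 × 28 = 560 also has 20.

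**4. Simulation (assumed inputs, not document figures).** Time on treatment was exponential with median 12, 18 or 24 months, cut at 24 months. Each patient's chance of completing a cycle was uniform on 0.9-1.0 or on 0.5-1.0. There were 200,000 patients per scenario. Among patients with room for at least one cycle, the number of cycles that fit explains 78-99% of the variance in the count, and the patient's conformity 0.2-14%.

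**5. Share with at least one completed cycle, same simulation.** When the conformity range widens from 0.9-1.0 to 0.5-1.0 (mean 95% to 75%), this share moves from 94.5% to 93.0%, 96.3% to 95.3%, and 97.2% to 96.4% for medians of 12, 18 and 24 months. A drop of 20 points in mean conformity shifts it by 0.8 to 1.5 points.

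**6. Weak points of the obvious replacements.**
- The share of patients with all started cycles completed falls with duration. Assuming 95% independent completion per cycle, 0.95^6 = 74% and 0.95^26 = 26%.
- If a last cycle cut short by progression or death counts as a failure, two otherwise fully conforming patients score 5/6 = 83% and 25/26 = 96%. With that cycle set aside, both score 100%.
- SAP section 7 imputes a missing day as the 15th, and applies the 15 August rule to dates such as cycle starts. A day-only imputation can be wrong by up to 31 − 15 = 16 days, more than half of a 28-day interval.

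**The case against.** The study is descriptive, with no hypothesis, and the count is reported as a distribution. Nothing in the SAP ranks patients by it or sets a conformity threshold. Dose reductions, temporary discontinuations, discontinuation with reasons, time to discontinuation and length of follow-up are also reported, so a reader is not left with the count alone. This stands, and it keeps the point small. Those measures are per patient, however: one pause in 26 cycles looks the same as thirteen.

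Three stronger readings are tempting, and the documents do not support them.
- A reader might infer that the count is blind to interruptions. It is not: if only full cycles count, an interrupted cycle lowers it. The defect is that this effect cannot be separated from duration.
- A reader might infer that the SAP has dropped the protocol's share of patients completing a cycle. It has gone from section 6 only; 8.2.2 (Proposed) and 8.2.9 still carry it. That is a conflict to reconcile. Nor do the documents say that the share means at least one cycle, so step 5 is conditional on that reading.
- A reader might infer that the SAP treats early progressors as non-conforming. No passage does.

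It is also fair that the posology item in the protocol rests on a cited product document outside these papers. Whether a delayed cycle departs from posology cannot be settled here, which is why the SAP needs its own stated rule for completion.

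**Conclusion.** The point holds in limited form. As listed in SAP section 6, the only cycle-schedule measure under the posology item is a count without a denominator, and it cannot separate conformity from time on treatment. Under full conformity it ranges from 6 to 26 between 6 and 24 months; this rests only on 28-day cycles and the 2-year window. The variance shares and the near-constant share with at least one completed cycle rest on the assumed distributions in step 4 and show direction, not this cohort's values.

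The consequence is a mislabelled descriptive result on one part of Secondary Objective 1. No test, primary result or survival estimate is affected. It is worth correcting because a better measure can be derived from data already specified for collection.

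**What to change.** In SAP section 6 and 8.2.2, and in the 8.2.9 table to match:

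- Relabel the completed-cycle count as treatment exposure and keep its summaries.
- As the posology measure, report the pooled percentage of started cycles completed, with a confidence interval that allows for clustering by patient, and the per-patient distribution of completed over started cycles. The pooled figure gives more weight to long-treated patients, so both are needed.
- Leave out of the denominator the cycle in progress at the data cut and a last cycle cut short by permanent discontinuation, progression or death. Report their numbers separately.
- State when a cycle counts as completed, consistent with the protocol's own description of a cycle, including how delayed and interrupted cycles are treated.
- If the share of patients with all started cycles completed is shown, give it over a fixed number of cycles, for example the first 6 started.
- Intervals between cycle starts may be summarised descriptively, using observed dates only. They show delays that completed over started can miss.
- Reconcile section 6 with 8.2.2 and 8.2.9 on the share of patients completing a cycle, and define that share if it is kept.

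Cost: the Actual paragraphs are in the past tense, so this means a small reanalysis as well as new wording. No new data are needed beyond the cycle dates listed in protocol 9.3, but some cycles will be lost to missing dates, and their number should be stated.
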